4.2 Accrual

The study will enroll a total of 90 patients at the Hospital of the University of Pennsylvania (HUP).

The study will be powered on the primary objective of the study, which is to compare adherence with twice daily blood pressure monitoring in subjects with and without a social incentive. Based on data in other study populations, we expect a 50% adherence rate in subjects without a social incentive.

A sample size of 90 subjects will provide 80% power to detect a 30% difference in adherence between groups. This calculation is based on a two-sample comparison of means, with $\alpha=0.05$.

Patients will be identified from the inpatient stroke service and the outpatient neurology clinic at the Hospital of the University of Pennsylvania. It is expected that we will complete enrollment in 15 months and the study will be completed in 2 years.

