6. DRUGS OR DEVICES

All patients will receive a Withings wireless blood pressure monitor. This commercially available device measures heart rate and blood pressure. The device is operated by and communicates with both Apple and Android smart phones (Apple iPhone 3GS and newer, Android 4.0 and newer) via bluetooth. Blood pressure and heart rate readings will be automatically uploaded to Penn’s *Way to Health* platform via the subject’s smart phone. There are no risks associated with this device. All subjects will be instructed on the proper use of the device as well as best practices for measuring blood pressure at the time of study enrollment.

Way to Health is an integrated research platform that uses online tools to connect with and collect data from wireless devices. Blood pressure and heart rate data will be collected and stored in a secure, HIPAA compliant format. The platform will provide automatic reminders for all patients to use the blood pressure cuff twice daily. Additionally, the platform will automatically apply the social incentive to randomized subjects. The social incentive is described in more detail later (section 7.1).

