Patients will be randomly assigned (1:1) to either receive a social incentive or not. The social incentive will require the subject to identify a social supporter. This individual can be a family member, friend, or other community member selected by the subject. The social supporter will need to assent to the study and register on the Way to Health platform. The social supporter will receive education on the importance of hypertension, how to measure blood pressure, and how to operate the Withings monitor. If the social supporter is not present at the time of subject enrollment, they may assent to the study via telephone and/or by registering online at the Way to Health platform. In this scenario they will receive education via telephone and/or online.

The social supporter will choose whether they prefer to receive study communications via text message or email. The social supporter will receive a text or email message alert at 11:00am if the subject has not completed their morning BP reading and at 9:00pm if the subject has not completed their evening BP reading. The social supporter will also receive feedback on the subject's BP control from the Way to Health platform on a weekly basis. This message will summarize the subject's adherence to home monitoring in the preceding 7 days. It will also contain the subject's mean BP over the preceding 7 days and note whether the subject's BP is above or below a goal of <140/90 mm Hg. The expectation is that the social support person will provide further feedback to the subject in order to improve both adherence and BP control.

Non-adherence

BP readings will be automatically uploaded from the subject's smartphone to the Way to Health platform. If the subject goes 7 days without a single BP measurement, Way to Health will alert study personnel. Study personnel will contact the subject by phone to remind them to check their BP and troubleshoot any potential technical

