8. STATISTICAL ANALYSIS

Demographics and past medical history variables will be summarized for all subjects using means or medians as appropriate for continuous variables and proportions for categorical variables. We will compare the two study arms using Student's t-test or Wilcoxon rank sum as appropriate for continuous variables and χ^2 test for categorical variables.

The primary outcome measure is adherence with blood pressure monitoring during the study period. Adherence will be defined by dividing the number of successfully completed BP measurements (numerator) by the expected number of BP measurements (denominator). The expected number of BP measurements is the number of days that the subject is in the study multiplied by 2. Most subjects will be enrolled in the study for 90 days and will therefore be expected to check their BP 180 times. Adherence in this case is the number of completed BP measurements divided by 180. The 90-day follow-up visit has a window of +/- 7 days, so for subjects that complete the study protocol the denominator will be adjusted accordingly. Subjects whom withdrawal from the study and/or stop monitoring their BP before the 90-day follow-up visit will remain in the analysis. These subjects will be considered non-adherent for all BP measurements after they cease taking measurements and the denominator will be set at 180. As an example, if a subject checks their BP 60 times in the first 75 days of the study and then ceases all BP measurements, adherence will be calculated as $60/180=33.3\%$. After adherence has been calculated for all subjects we will evaluate the distribution of adherence for normality and compare adherence between the two study arms using Student's t-test or Wilcoxon rank sum as appropriate. A sample size of 90 will give us 80% power to detect a 30% difference between groups with $\alpha=0.05$.

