Additional analysis will compare the change in blood pressure between the two groups. The mean systolic and diastolic blood pressure in the first 7 days of the 90 day study period and the last 7 days of the 90 day study period will be calculated for each subject. The average change in blood pressure will be compared between study arms using Student's t-test or Wilcoxon rank sum as appropriate. We will also compare the proportion of subjects with an average blood pressure <140/90 mm Hg in the final week of the study between groups using χ^2 . Subjects who drop out of the study or cease monitoring their BP prior to day 90 will be included in these analyses if they have a minimum of 14 days of monitoring. For these subjects, we will utilize BP readings from the last 7 days of monitoring. The use of earlier readings carried forward should be conservative and bias the results toward the null. Exclusion of subjects with less than 14 days of monitoring may truncate our sample and introduce bias, so we will conduct a sensitivity analysis in which we impute a change in BP for subjects with less than 14 days of monitoring of zero.

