10.2 Potential Study Benefits

This study has the potential to benefit all subjects. Hypertension is the most important modifiable risk factor for stroke and an important risk factor for myocardial infarction, chronic kidney disease, and other serious medical conditions. Study education about the importance of hypertension, goal blood pressure levels, and regular monitoring of blood pressure may lead to improved blood pressure control in subjects, which in turn has the potential to lower the risk of serious medical conditions, including heart attack and stroke. There is also a potential societal benefit, as this study will provide important insights into adherence with home monitoring in patients with cerebrovascular disease and may be useful for future larger studies which combine home monitoring with therapeutic interventions to lower blood pressure with the goal of reducing the risk of future stroke.

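### Section 8 says carried-forward home BP readings bias toward the null, but the direction depends on unstated conditions and can reverse if controls stop monitoring earlier

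*Combined protocol and SAP*

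**What the plan says.** Section 8 compares between arms the change in mean home BP from the first 7 days to the last 7 days of the 90-day period, and the proportion below 140/90 mmHg in the final week. Subjects who stop early but have at least 14 days of monitoring are kept: "For these subjects, we will utilize BP readings from the last 7 days of monitoring". The plan then gives its view of the direction of bias: "The use of earlier readings carried forward should be conservative and bias the results toward the null". Subjects with less monitoring are left out, with one sensitivity analysis in which "we impute a change in BP for subjects with less than 14 days of monitoring of zero".

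Four other parts of the protocol bear on this:

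- For the primary endpoint, Section 8 treats stopping as non-adherence: "These subjects will be considered non-adherent for all BP measurements after they cease taking measurements".
- Section 4.2 plans for a large adherence difference: "A sample size of 90 subjects will provide 80% power to detect a 30% difference in adherence between groups".
- Section 7.1 (Social Incentive) expects supporters to give feedback "in order to improve both adherence and BP control".
- Section 10.2 anticipates benefit for all subjects, partly because "regular monitoring of blood pressure may lead to improved blood pressure control in subjects".

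Clinic BP, the mean of three readings, is taken at enrolment (Section 7.1) and at day 90 (Section 7.4). Section 8 names no analysis of it.

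**The concern.** Carrying an early reading forward understates a subject's change when BP is still falling. The effect on the between-arm comparison depends on which arm loses more of its fall. The incentive is designed to raise adherence and stopping is one form of non-adherence, so more or earlier stopping in controls is plausible. Both arms also receive education, a cuff, reminders and weekly feedback, so a fall in both arms is plausible too.

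Three conditions together push the bias away from the null: controls stop more or earlier, the two arms fall by similar amounts, and BP would go on falling after monitoring stops. Late incentive-arm readings are then compared with earlier control readings, and a benefit can be created or enlarged. Readers have been told to expect the opposite, so they would over-trust a positive signal in a pilot meant to inform later BP studies.

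A difference that arises because the incentive keeps people monitoring, and monitoring lowers their BP, is a real effect and not part of this concern.

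**Working it through.** The plan states a direction and no figure, so there is no number to reproduce. The check is of sign first, then size.

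**Sign.** Let D be the incentive-arm fall minus the control fall, so that positive favours the incentive. If BP keeps falling after stopping:

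bias in D = (control stoppers' share × their unobserved remaining fall) − (incentive stoppers' share × their unobserved remaining fall)

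Nothing fixes the sign of this difference.

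**Inputs from the documents.** 90 subjects allocated 1:1 (45 per arm); 7-day windows at each end of 90 days; 14-day minimum; zero-change sensitivity analysis.

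**Assumed inputs (not in the documents).** Stop time uniform on days 1 to 90; linear fall, quoted over 90 days; SD of change 12 mmHg. The SE of the arm difference is 12 × √(2/45) = 2.5, or about 2.6 after exclusions.

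**Formula.** The window midpoints are day 3.5 and day 86.5. A share 76/89 = 85% of stoppers reach day 14. Their mean stop is day 52, so their last window is centred on day 48.5 and they miss 86.5 − 48.5 = 38 of 90 days, or 0.42 of the fall. The stoppers' share of an analysed arm, at stopping rate p, is 0.85p / (1 − p + 0.85p): 18%, 27%, 36% and 46% for p = 20%, 30%, 40% and 50%. Then:

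bias = 0.42 × (control share × control fall − incentive share × incentive fall)

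For a common 10 mmHg fall at 50% vs 20% stopping: 0.42 × (0.46 − 0.18) × 10 = 1.2 mmHg.

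**No true effect, fall continues after stopping** (20,000 simulated trials per row, t-test at 0.05):

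| Stopping, control vs incentive | Fall (mmHg) | Spurious benefit (mmHg) | Type I error | With zero imputation |
|---|---|---|---|---|
| 30% vs 20% | 10 | 0.4 | 5.2% | 0.5; 5.3% |
| 40% vs 20% | 10 | 0.8 | 5.8% | 1.0; 6.6% |
| 50% vs 20% | 10 | 1.2 | 7.3% | 1.5; 8.9% |
| 50% vs 20% | 5 | 0.6 | 5.6% | – |
| 50% vs 20% | 15 | 1.8 | 10.0% | 2.2; 13.3% |
| 50% vs 20%, front-loaded (20-day time constant) | 10 | 0.4 | 5.3% | – |

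The planned sensitivity analysis leaves the carried-forward values untouched and, in these settings, adds to the bias.

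Stopping times concentrated early give more. Suppose 40% of controls stop at day 30, 15% of the incentive arm stop at day 60, and both arms fall 10 mmHg over the 83 days between window midpoints. The spurious benefit is 0.40 × 10 × 60/83 − 0.15 × 10 × 30/83 = 2.35 mmHg, with type I error 14.4% at SD 12.

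**Where the plan is right.** Over the 83 days, falls of 10 vs 15 mmHg give a true difference of 5 × 83/90 = 4.6.

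- Equal 30% stopping: the bias is 0.42 × 0.27 × (10 − 15) = −0.6, so 4.6 becomes 4.0.
- Equal 50% stopping: 4.6 becomes 3.6.
- 50% vs 20% stopping with falls of 3 vs 10: 6.5 becomes 6.3.

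The bias runs away from the null only while the incentive-arm fall is below about 2.6, 2.1 or 1.5 times the control fall, at 50%, 40% or 30% vs 20% stopping. There is no bias if stopping and falls are both equal, or if BP has no trend.

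**BP course after stopping** (50% vs 20%, 10 mmHg). Carry-forward shows 1.2 whatever happens next. The true difference is 0 if the fall continues, 0.7 at half pace, 1.4 if BP levels off and 2.1 if half the fall is lost. The first two give bias away from the null and the last two toward it. Before rounding, the levelling-off value is 1.37, so the switch comes when about 1 − 1.20/1.37 = 12% of the remaining fall still occurs.

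**The case against.** The strongest reply has four parts.

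- **The effect is small.** In most scenarios it is well under one standard error. Among the uniform-stopping scenarios, type I error reaches 10% under the main analysis only with 50% vs 20% stopping and a 15 mmHg linear fall that continues unchanged. It concerns one hedged sentence about a secondary endpoint in a single-centre pilot.
- **The adverse case sits awkwardly with the trial's premise.** The protocol credits monitoring itself with BP benefit, and subjects who decline to continue lose their alerts and return the device (Section 7.1, Non-adherence). Levelling off or rebound after stopping is then plausible, and the plan's sentence would be about right.
- **Differential stopping is not documented.** The planned adherence difference could come entirely from scattered missed readings, which do not trigger carry-forward. Section 6 says: "The platform will provide automatic reminders for all patients to use the blood pressure cuff twice daily". Staff also make contact after 7 days without a reading.
- **The clinic comparison may be incomplete,** because subjects who stop are only encouraged to attend day 90.

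All four stand as limits on size and likelihood. None supplies the missing condition. A continuing fall after stopping remains possible, for example through ongoing physician treatment, and the hedge in the plan's wording does not tell a reader when the expectation fails. The planned sensitivity analysis cannot reveal the problem.

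**Conclusion.** The concern holds. The direction of carry-forward bias is not guaranteed, and the plan's unconditional expectation is unsupported. Confidence in that is high. Confidence in the size is low to moderate, because stopping rates, the SD, the fall and the BP course after stopping are all assumed. For moderate differences in stopping, the spurious benefit is roughly 0.4 to 1.2 mmHg on a 10 mmHg shared fall, with a modest rise in type I error; it is larger if controls stop early and together or if the shared fall is bigger. The final-week proportion below 140/90 uses the same carried-forward readings and shares the weakness. The primary adherence endpoint and the sample size are unaffected.

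**What to change.** 1. In Section 8, delete the sentence on conservatism or state its conditions. For example: the bias is toward the null when stopping is similar in both arms and the incentive has a real effect, and may run the other way if controls stop earlier and BP would have continued to fall.
2. Add a sensitivity analysis comparing day-90 clinic BP between arms, adjusted for enrolment clinic BP, in all randomised subjects who attend, whether or not they kept monitoring.
3. Report by arm how many subjects stopped monitoring, when they stopped, and how many of them attended day 90.

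A repeated-measures model of weekly home BP means is an optional further check. The planned home BP analysis can stay.

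The cost is one sentence of wording and a little more analysis, with no new data collection. The drawback is that day-90 attendance among subjects who stopped may be incomplete, so the clinic comparison may also have gaps; item 3 makes that visible.

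### The only BP sensitivity analysis fixes change at zero for everyone with under 14 days of monitoring, which can favour the incentive arm if more controls stop early and early stoppers' BP falls similarly in both arms

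*Combined protocol and SAP*

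**What the plan says.** Change in BP over 90 days is a secondary endpoint (section 2.2). Section 8 builds it from home readings: "The mean systolic and diastolic blood pressure in the first 7 days of the 90 day study period and the last 7 days" of that period are averaged for each subject, and "The average change in blood pressure will be compared between study arms using Student's t-test or Wilcoxon rank sum as appropriate".

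Section 8 then handles incomplete monitoring in three ways:

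- **Stopped, but at least 14 days of monitoring:** included. "For these subjects, we will utilize BP readings from the last 7 days of monitoring". The plan adds: "The use of earlier readings carried forward should be conservative and bias the results toward the null".
- **Under 14 days, main analysis:** left out. The plan concedes: "Exclusion of subjects with less than 14 days of monitoring may truncate our sample and introduce bias".
- **Under 14 days, sensitivity analysis:** "we impute a change in BP for subjects with less than 14 days of monitoring of zero".

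No other sensitivity analysis for BP appears. The claim of bias toward the null is made for carried-forward readings, not for the zero.

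Two other places bear on this. Section 7.1 gives only the incentive arm a supporter who is alerted to missed readings: "The expectation is that the social support person will provide further feedback to the subject in order to improve both adherence and BP control". Section 10.2 says that education and regular monitoring "may lead to improved blood pressure control in subjects", without separating the arms and without a figure.

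**The concern.** A sensitivity analysis should show whether the main result survives other plausible assumptions about the missing values. A single constant tests one assumption, and it enters the values as if observed, with no uncertainty attached.

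In most trials a constant for early stoppers would be a small matter. Here, early stopping is close to the behaviour that is randomised. If the incentive works on adherence, fewer incentive subjects may fall under 14 days, so fewer of them receive a zero. If BP is falling for reasons common to both arms (education, reminders and weekly feedback go to everyone), each zero pulls its arm's mean fall down, and the control mean is pulled down more.

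The check could then show a BP benefit that does not exist, or appear to confirm one found in the main analysis. Agreement between the two could not be read as robustness.

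**Working it through.** **Inputs from the documents.** 90 subjects (section 4.2) allocated 1:1 (section 7.1), so 45 per arm; t-test or rank sum test on change (section 8). The documents give no stopping rates, expected fall, SD or power for BP change, so there is no BP figure of the plan's to reproduce.

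**Assumed inputs.** Share with under 14 days: 5-10% incentive, 10-30% control. Common fall: 5-10 mm Hg. SD of change: 10-12 mm Hg, with 15 as a wider case. No true arm difference.

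**Formula.** Let p be the share of an arm with under 14 days and m the true mean fall among those subjects (C control, I incentive). Replacing their change by zero lowers the arm's mean fall by p × m. The error in (incentive fall minus control fall) is therefore

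bias = pC × mC − pI × mI,

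which becomes (pC − pI) × m when early stoppers fall by the same m in both arms.

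**Results with a common fall.** Bias is from the formula; type I error is from simulation of a t-test at 0.05 with 45 per arm and SD 10-12.

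| Control v incentive under 14 days | Fall (mm Hg) | False benefit (mm Hg) | Type I error |
|---|---|---|---|
| 10% v 5% | 8-10 | 0.05 × 8 to 0.05 × 10 = 0.4-0.5 | 5-6% |
| 20% v 10% | 5-8 | 0.10 × 5 to 0.10 × 8 = 0.5-0.8 | 6-7% |
| 30% v 10% | 5 (SD 12) | 0.20 × 5 = 1.0 | about 7% |
| 30% v 10% | 8-10 | 0.20 × 8 to 0.20 × 10 = 1.6-2.0 | 10-17% |
| 20% v 20% | 8 | 0 | 5% |

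A larger SD dilutes the effect: at SD 15, the 30% v 10% case gives about 9% (fall 8) and 10-11% (fall 10). Leaving early stoppers out gave bias near 0 and type I error near 5%, provided stopping is unrelated to BP change.

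**Where the bias vanishes or reverses.**

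- Early stoppers did not change: mC = mI = 0, bias 0.
- All stopping occurs after 14 days: nobody receives a zero, bias 0.
- More incentive subjects stop early (10% control v 20% incentive, fall 10): 0.10 × 10 − 0.20 × 10 = −1.0 mm Hg.
- Control stoppers fall much less (20% with fall 2 v 10% with fall 8): 0.20 × 2 − 0.10 × 8 = −0.4 mm Hg.

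**The case against.** The strongest reply is that zero may be right. A subject who declines further monitoring has alerts stopped and returns the cuff (section 7.1, Non-adherence), so early stoppers may not improve at all. With 30% v 10% stopping and a fall of 8 mm Hg among continuers only, the arm means are 0.7 × 8 = 5.6 and 0.9 × 8 = 7.2. The difference of 1.6 mm Hg is then a real effect of keeping people monitoring, and an imputation model built on continuers would tend to remove it. This stands: the documents do not say which case holds. That is a reason to show a range; it does not justify zero alone.

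Zero is also close to an extension of the plan's own rule. With 7 or fewer days of readings the first-week and last-week windows coincide, so carrying forward gives exactly zero; with 8-13 days the windows overlap and the change is damped. This stands as an explanation of where zero comes from, but it does not make zero a good estimate of change at day 90.

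A reader might go further and infer that the check produces a false benefit whenever BP falls in both arms and controls stop earlier. The documents do not support that. Controls who stop after 14 days are carried forward and never receive a zero. A reader might also infer that the plan predicts a fall in both arms. Section 10.2 says only that control may improve, and screening BP above 140/90 adds little because change is measured from the first week of home readings.

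Finally, 30% of controls stopping before day 14 is at the high end, given reminders in both arms, a call at 48 hours and staff contact after 7 silent days. This stands, and the lower rows of stopping rates show little inflation.

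**Conclusion.** The point holds in a conditional form and is minor. Fixing the change at zero can create a false incentive benefit if two things are true together: more controls than incentive subjects have under 14 days, and early stoppers' unobserved BP falls similarly in both arms. Otherwise it may be unbiased or may favour control. Across the assumed inputs the effect ranges from negligible to a type I error two to three times nominal; none of those inputs comes from the documents.

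Only a sensitivity analysis of a secondary endpoint is affected. The adherence result does not depend on it, and nothing here shows that the main BP comparison is wrong. What the plan lacks is a check that can answer the question it raises about excluding early stoppers.

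**What to change.** In section 8, before arm-level data are seen:

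1. **Use the clinic readings.** BP is averaged over three readings at enrollment and again at day 90 (sections 7.1, 7.4 and 7.5), and subjects who stop home monitoring are kept in follow-up. Section 8 does not use these readings. Add a sensitivity comparison of change in clinic BP from enrollment to day 90, adjusted for enrollment BP, in all who attend, including those who stopped home monitoring. Report attendance by arm, because non-attenders are still missing.
2. **Replace the single zero with a range.** For subjects with under 14 days, multiply impute the change given enrollment BP and any first-week readings. Then shift the imputed values by arm to find the point at which the conclusion changes. Keep zero as one labelled point, noting that it favours the arm with fewer early stoppers if BP falls in both arms.

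The cost is SAP wording and a little programming, with no new data. Intervals will be wider, and readers get a range in place of one figure. If the imputation draws on the control arm only, the test becomes conservative: simulated type I error was 2.4-3.7%, so some power is lost.

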We will compare secondary outcomes across study arms including number of calls to the study team, number of physician visits, number of emergency department visits, number of changes in antihypertensive medications, and the patient perception of: study protocol, utility of blood pressure monitoring, and blood pressure control. We will also determine the relationship between adherence to blood pressure monitoring and change in blood pressure during the study period. For this analysis, we will first determine the average adherence in the study population. We will compare the change in blood pressure in those with above average adherence to those with below average adherence. This will be done in the full study population and then stratified by study arm. In an exploratory analysis multivariable regression will be utilized to determine which factors were associated with a high level of adherence to the study protocol, defined as adherence above the study median. We will investigate the following variables in a univariate analysis: age, sex, race, ethnicity, income, social support in the home, employment status, MMSE score, NIHSS, and modified Rankin Scale. Variables in the univariate analysis with $p < 0.10$ will be incorporated into a multivariable logistic regression model. We will test for an interaction between the social incentive and the variables in the multivariable model.

9. Data Handling and Record Keeping

9.1 Confidentiality.

- Paper-based records will be kept in a secure location and only be accessible to personnel involved in the study.
- Computer-based files will only be made available to personnel involved in the study through the use of access privileges and passwords.
- Prior to access to any study-related information, personnel will be required to sign statements agreeing to protect the security and confidentiality of identifiable information.
- Whenever feasible, identifiers will be removed from study-related information.

- A Certificate of Confidentiality will be obtained, because the research could place the subject at risk of criminal or civil liability or cause damage to the subject's financial standing, employability, or liability.
- A waiver of documentation of consent is being requested, because the only link between the subject and the study would be the consent document and the primary risk is a breach of confidentiality. (This is not an option for FDA-regulated research.)

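### Both parts of the secondary objective are analysed only with adherence split in two (at the average, then at the median); an unsplit analysis of the same data would be more informative

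*Combined protocol and SAP*

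**What the plan says.** Section 1.2 sets a two-part secondary objective: whether adherence is associated with blood pressure change, and which individual factors are associated with adherence. The last part of Section 8 is the only text that analyses either.

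- **Blood pressure change.** The plan says "we will first determine the average adherence in the study population", and then "We will compare the change in blood pressure in those with above average adherence to those with below average adherence". It adds: "This will be done in the full study population and then stratified by study arm". It does not say whether the average is a mean or a median, or whether the by-arm step reuses the study-wide cut or takes a new one within each arm.
- **Predictors.** An exploratory multivariable logistic model is used "to determine which factors were associated with a high level of adherence to the study protocol, defined as adherence above the study median", after univariate screening at p < 0.10.

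Adherence is left unsplit only in the primary comparison, where "we will evaluate the distribution of adherence for normality and compare adherence between the two study arms". That answers the primary objective.

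Two other rules in Section 8 matter here. The adherence denominator is fixed at 180 for anyone who stops monitoring early. In the between-arm blood pressure analyses, early stoppers "will be included in these analyses if they have a minimum of 14 days of monitoring", and their final value then comes from the week before they stopped. I assume that these blood pressure rules carry over to the adherence analysis, for which none are stated.

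**The concern.** Adherence is recorded on a scale with up to 181 values (0 to 180 readings). Cutting it in two treats a subject just above the average like one who never missed a reading, and unlike one just below it. In a 90-subject pilot that costs precision when the relation is roughly linear.

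It also limits what can be carried forward. Section 5.2 says that the trial is meant to inform later studies. An above-versus-below difference depends on where this sample's average happens to fall. A slope per 10 points of adherence, with its confidence interval, is easier to use in another population.

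**Working it through.** **The plan's own figure.** Sections 4.2 and 8 state 80% power with 90 subjects for a 30% difference, by a comparison of means at alpha 0.05. That concerns the primary comparison; no figure is given for the secondary objective. No SD is stated, so the 90 cannot be rebuilt by the named method. Solving backwards for 30 points, two-sided, SD = 0.30 / (2.80 × √(2/45)) ≈ 0.51. This does not show the 90 to be wrong, and the power figures below do not rest on it.

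**Inputs.** From the documents: n = 90, 1:1 allocation and alpha 0.05. Assumed: two-sided testing, nobody lost to the 14-day rule, the shape of adherence, and the correlation r with blood pressure change.

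**Step 1: information kept by a mean split.** Under a linear relation this is k, the squared correlation between adherence and its above-mean indicator. These three shapes are symmetric, so a median split gives the same k.

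| Assumed shape | k | Lost |
|---|---|---|
| U-shaped, Beta(0.5, 0.5) | 8/π² = 0.811 | 19% |
| Uniform | 0.750 | 25% |
| Normal | 2/π = 0.637 | 36% |

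Under normality, 90 subjects act like 90 × 0.637 ≈ 57. These are illustrations, not bounds: a more extreme U-shape, Beta(0.3, 0.3), has k = 0.857 and loses 14%.

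**Step 2: power.** Fisher's z gives power = Φ(atanh(r√k) × √(n − 3) − 1.96), with √87 = 9.33. At r = 0.30:

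- unsplit: atanh(0.300) = 0.310, so Φ(0.93) = 82%
- U-shaped, split: atanh(0.270) = 0.277, so Φ(0.62) = 73%
- uniform, split: atanh(0.260) = 0.266, so Φ(0.52) = 70%
- normal, split: atanh(0.239) = 0.244, so Φ(0.32) = 62%

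Simulation (20,000 runs) agrees: about 83% unsplit, and 75%, 71% and 64% split. With normal adherence (4,000 runs), power goes from about 49% to 34% at r = 0.20, and from about 98% to 88% at r = 0.40.

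**Step 3: predictor model.** Take one 50/50 factor (45 versus 45), beta-distributed adherence with SD 0.20 to 0.35, and an effect that gives a t-test about 80% power (10,000 runs).

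| Adherence centred at | t-test | Rank test | Median split |
|---|---|---|---|
| 50% | about 80% | 78–83% | 55–58% |
| 65% | about 80% | 82–96% | 59–84% |

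The gain depends on shape. At 65% with SD 0.35, the median split (84%) beats the t-test (80%), while the rank test reaches 96%.

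**Step 4: does unsplit adherence bring its own problem?** Early stoppers keep a denominator of 180, and their last blood pressure week comes earlier. Low adherence is therefore tied to a shorter interval between the two weeks. The simulation assumed no adherence effect, a linear 10 mmHg fall in everyone, SD 12 mmHg, and 20–30% stopping between days 14 and 89. Unadjusted continuous adherence was significant in 21–32% of runs and the mean split in 12–20%. Adjusting for monitoring duration, or restricting to full-duration monitors, brought the continuous analysis back to about 5%.

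**The case against.** The strongest reply is that the plan is inefficient rather than invalid. This is a pilot, the primary comparison keeps adherence unsplit, and the predictor model is labelled exploratory. The correlation of 0.30 is chosen: at 0.20 both analyses are weak and at 0.40 both are adequate. All of that stands and sets the priority. It does not remove the point, because the blood pressure analysis serves a stated secondary objective and is not labelled exploratory.

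A second reply is that part of what a continuous analysis detects may be artefact. Step 4 shows that this is right. The split shares the problem but flags it less often, so an unsplit analysis is an improvement only if monitoring duration is handled.

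A reader might also infer that one study-wide cut leaves lopsided groups within each arm and so damages the by-arm analysis. The documents do not support this, for two reasons.

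- Section 8 does not settle whether the cut is study-wide or arm-specific.
- Large imbalances need inputs that clash with the trial's own sizing. With 45 per arm, a 30-point gap and an SD of 0.20 to 0.35, primary power would be 98% or more, not the stated 80%. Reading the 30% as relative (50% versus 65%) fits 80% power at an SD of about 0.15/0.597 = 0.25. A study-wide cut then loses about 30% in control and 27% in the incentive arm, against about 28% with arm-specific cuts, so the choice of cut hardly matters.

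**Conclusion.** The point holds as a cheap improvement of low-to-moderate priority. Both parts of the secondary objective rest solely on split adherence. If the relation with blood pressure change is roughly linear, the split loses about 19–36% of the information under the shapes tried. At a correlation of 0.30 and n = 90, that takes power from about 82% to 62–73%. These sizes depend on assumed shapes and correlations. For the predictor model the gain ranges from large to none against a t-test, which is why the method matters.

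No by-arm harm from lopsided groups is claimed, and nothing here casts doubt on the primary analysis.

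**What to change.** **(a) Adherence and blood pressure change.** Make the main analysis a linear regression of last-7-day mean home blood pressure on continuous adherence (per 10 points), first-7-day mean home blood pressure and arm, with Section 8's blood pressure definitions and 14-day rule. Add the interval between the two blood pressure weeks (days monitored) as a covariate, or repeat the analysis in subjects who monitored to the 90-day visit. Report the slope with its 95% CI overall and within each arm, check linearity with a plot, and describe the slope as an association. Keep the above/below-average comparison as descriptive, and state whether the average is a mean or a median and whether the cut is study-wide or arm-specific.

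**(b) Exploratory predictor model.** Use unsplit adherence as the outcome with arm as a covariate. Name one method in advance that tolerates skew, for example proportional-odds regression. Keep the planned interaction test.

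**Cost.** A revision of Section 8 before analysis, with no new data. It is more than a change of words, since the models change. Part (a) assumes rough linearity, and adjusting for interval removes part of the variation in adherence, so some of the gain in precision is given back.
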